Study Title: Neurofeedback for Stroke Rehabilitation

NCT: 03775915

Chief/Principal Investigator: [name], Wellcome Centre for Integrative Neuroimaging, University of Oxford

Trial manager: [name], Wellcome Centre for Integrative Neuroimaging, University of Oxford

Sponsor: The University of Oxford

Protocol summary – 10th June 2021

Summary of Study Design

Real-time neurofeedback aims to alter brain activation patterns through online feedback of ongoing brain activity using magnetic resonance imagining (MRI). Stroke survivors will be randomised to receive 3 sessions of real or sham neurofeedback. This study aims to investigate whether: 1) stroke survivors can maintain alterations in brain activity after the feedback is removed, 2) neurofeedback training leads to improvements in movement of the hand and arm, 3) neurofeedback training leads to changes in brain structure and function, 4) variability in response across people can be understood.

The training will consist of 3 real time functional MRI (rtfMRI) training sessions. Baseline measures will be taken prior to the start of the first session and post-training measures will be taken after the final training session.

Primary and Secondary Endpoints/Outcome Measures

The primary outcome measures are a change in motor function in the neurofeedback group compared to the control group and changes in brain activity during neurofeedback. These outcome measures will address whether the neural plasticity brought about by the neurofeedback can lead to subsequent behavioural improvements.

The secondary outcome measures will be performance on visuo-motor tasks (visually cued grip force), motor impairment and measures of change in brain structure and function.

Study Participants

Patients who have had a stroke more than 6 months previously, that has affected their motor function of their upper limb.

Inclusion Criteria:

- Participant is willing and able to give informed consent for participation in the study.
- Participant can understand verbal and written instructions in English.

- Male or Female, aged > 18 years
- Patient will have had symptomatic stroke that has affected the upper limb of one side of their body
- Patients must have some residual movement in their affected limb.

Exclusion Criteria:

- Contraindications to MRI, such as a pacemaker, metallic implants or aneurysm clips
- Inability to provide informed consent
- Inability to actively participate in the research procedures

Study Procedures

Written informed consent will be taken at the start of the first session by an experimenter trained in good clinical practice (GCP). A number of baseline measures of motor and neural function will then be performed. These tests will then be followed by the training sessions where participants will receive real or sham neurofeedback while performing a motor skill with their affected hand. Following the training sessions, the post-test session will repeat the motor and neural measures performed during baseline.

Number of Participants

The sample size (n=30) was selected to ensure there was sufficient data given issues in data quality or participant retention. In most fMRI studies it is recommended that there be at minimum 12 participants in each group (e.g., sham vs. treatment) (Desmond & Glover, 2002).

Analysis of Endpoints

MR analysis will be performed using a common approach, using the FMRIB Software Library. EEG analysis will be performed similarly using a common approach using EEGLab software for Matlab.

Statistical analysis of derived data will be performed using SPSS Statistics for Mac and MATLAB/R. Behavioural (e.g., Jebsen Taylor test, Action Research Arm Test) and EEG outcome measures will be assessed across sessions using a mixed-ANOVA (or linear mixed model as appropriate) with group (real vs sham) as a between-subjects variable and session as a within-subjects variable. Behavioural outcomes will also be correlated with neurological changes over training.

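### Does the brain-activity primary outcome lack a real-versus-sham test?

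*Combined protocol and SAP*

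**What the plan says.** The Primary and Secondary Endpoints/Outcome Measures section puts both primaries in one sentence. The first is a change in motor function in the treated group; the sentence then continues "compared to the control group and changes in brain activity during neurofeedback". Read grammatically, the comparator belongs to the motor outcome, and the brain-activity outcome has none.

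In Analysis of Endpoints, MRI data receive one sentence: "MR analysis will be performed using a common approach, using the FMRIB Software Library". The inferential model comes in a separate sentence: "Behavioural (e.g., Jebsen Taylor test, Action Research Arm Test) and EEG outcome measures will be assessed across sessions using a mixed-ANOVA" (or a linear mixed model as appropriate), "with group (real vs sham) as a between-subjects variable and session as a within-subjects variable". The one remaining analysis is "Behavioural outcomes will also be correlated with neurological changes over training", which has no group factor.

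The design is stated plainly in Summary of Study Design: "Stroke survivors will be randomised to receive 3 sessions of real or sham neurofeedback". The same section says that "Baseline measures will be taken prior to the start of the first session and post-training measures will be taken after the final training session", and Study Procedures adds that "the post-test session will repeat the motor and neural measures performed during baseline".

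**The concern.** Training is delivered by real-time functional MRI, so the obvious source for the second primary is the data type that the model sentence leaves out. Read literally, a primary outcome has neither a comparator nor a test.

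Two things would be at stake. First, without a comparator, a change across sessions in the real arm alone might be reported as success, although practice or familiarity with the scanner could produce it in both arms. Second, even if real versus sham is understood, the motor model does not carry over unchanged. Motor measures have a pre-training value, so their group-by-session interaction compares change from baseline. Activity during feedback is seen in three sessions that all include real or sham feedback. The group term then asks whether the arms differ on average, and the interaction asks whether the difference varies over sessions. An analyst free to claim on either would have two chances at a positive result; one held to the wrong term could miss a true effect.

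**Working it through.** **Inputs from the documents.** Total sample 30; a minimum of 12 per group cited for fMRI studies (Number of Participants); three training sessions; two arms. No allocation ratio, effect size, standard deviation, correlation or significance level is given.

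**Assumptions for illustration.** Allocation 1:1 (n = 15 per arm), two-sided 0.05, single-session SD of 1, equal correlation r between sessions, and d_j the real-minus-sham difference at session j.

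**1. Text.** The three parts of the concern are correct: no comparator is attached to the second primary, the model sentence lists behavioural and EEG measures only, and no term is singled out. No sentence says that brain activity will be judged within one arm, or that either of two terms will suffice. The plan is silent on these points and does not contradict its design.

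**2. False positives if either term may support the claim.** With normal data and compound symmetry the two tests are close to independent: 1 − 0.95² = 9.75%. Simulation with no true effect (60,000 runs, r = 0.5) gives 9.8% at n = 15 and 9.7% at n = 12. The arithmetic is sound, but the either-term rule it needs is not in the plan.

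**3. False positives if only one arm is examined.** Suppose both arms change equally by g standard deviations of change, so there is no real-versus-sham effect. A within-arm t test with n = 15 has noncentrality g√15: 1.16 at g = 0.3 and 3.10 at g = 0.8. It is significant with probability 19% and 82%. A session main effect in all 30 participants is significant with probability 36% and 99%. These are hazards of a reading that disregards the randomised sham arm.

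**4. Power by term.**
- Group term: noncentral t on 2n − 2 df, noncentrality mean(d) × √(n/2) / √((1 + 2r)/3).
- Interaction: noncentral F on 2 and 2(2n − 2) df, λ = (n/2) × Σ(d_j − mean d)² / (1 − r).

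Example, n = 15, r = 0.5, d = 0, 0.4, 0.8: the group noncentrality is 0.4 × 2.739 / 0.816 = 1.34, and λ = 7.5 × 0.32 / 0.5 = 4.8.

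| Real − sham over sessions 1–3 (SD), n = 15 | r | Group | Interaction |
|---|---|---|---|
| 0.8, 0.8, 0.8 | 0.5 | 74% | 5% |
| 0, 0.4, 0.8 | 0.5 | 25% | 47% |
| 0, 0.4, 0.8 | 0.7 | 22% | 69% |
| 0, 0.4, 0.8 | 0.3 | 31% | 35% |
| 0, 0.4, 0.8 | 0.2 | 34% | 31% |
| 0.2, 0.5, 0.8 | 0.5 | 37% | 28% |
| 0.4, 0.6, 0.8 | 0.5 | 49% | 15% |

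With 12 per arm and r = 0.5, the sustained pattern gives 63% and 5%, and growth from zero gives 21% and 38%. For a sustained effect the interaction carries no signal. For a growing effect it is clearly ahead only if the arms are equal at session 1 and the correlation is moderate or high.

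**5. Splitting alpha between the terms.** Testing each at 0.025 gives 1 − 0.975² = 4.9%, for this primary only. With the motor primary also tested at 0.05, and independent, the chance of at least one false positive is 1 − 0.95 × 0.9506 = 9.7%. The split also lowers power for the sustained pattern from 74% to 64%.

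**The case for a change.** The strongest case for a change grants that real versus sham is intended and says that this does not finish the job. Group-by-session is the usual reading of such a model, but it suits outcomes with a pre-training value. If real feedback shifts activity from the first session and holds it there, the conventional term has 5% power where the group term has 74%. A sentence naming the comparator and the term would cost no participants or scans. EEG is also brain activity, but the endpoint section does not name it, so the EEG wording is no sure rescue.

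Much of this stands. The text is incomplete, and the sustained pattern does behave as described. Three points keep it from being an error.

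- The two terms are not the only candidates. Neural measures are taken at baseline and repeated after training, and the endpoint speaks of changes, so a between-arm contrast referenced to baseline is also a possible reading.
- No single term is best in all cases. Which has more power depends on the effect's shape and on a correlation that the documents do not give. The choice, like that of region and contrast, turns on the scientific claim and belongs to the sponsor.
- The figures that look damaging describe analyses the plan does not propose: claiming on either term, or judging the real arm alone.

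**Conclusion.** No change to the plan follows. The second primary has an unwritten specification, not a wrong rule, and a trial statistician would fill it by comparing real with sham, as the randomised design requires, and by treating within-arm and session-only changes as descriptive. The 9.75% false-positive rate is conditional on a rule found nowhere in the text. The contrast of 74% with 5% rests on assumed values: 15 per arm, a sustained 0.8 SD and r = 0.5. For growing effects the gap narrows or reverses.

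This conclusion rests on two readings: that the sham arm is there to be compared with the real arm for brain activity as well as for movement, and that a text headed as a protocol summary need not carry every contrast. Whether a fuller plan records the region, contrast and term cannot be judged from these documents. A report that claimed this primary on a real-arm change alone, or on whichever term reached significance, would deserve criticism, but for a choice made in the analysis and not for anything the plan prescribes.

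### Motor outcomes measured before and after training: the group-and-session model is valid but estimates no baseline slope; ANCOVA would usually be more precise, by an amount the documents do not let us fix

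*Combined protocol and SAP*

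**What the plan says.** The document is a protocol summary, and its analysis text is short. Under Analysis of Endpoints, behavioural outcomes (the Jebsen Taylor test and the Action Research Arm Test are given as examples) are to be "assessed across sessions using a mixed-ANOVA (or linear mixed model as appropriate) with group (real vs sham) as a between-subjects variable". Session is the repeated factor. These are the only model terms given.

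Three other sections bear on the point:

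- **Primary and Secondary Endpoints/Outcome Measures:** "The primary outcome measures are a change in motor function in the neurofeedback group compared to the control group", together with changes in brain activity.
- **Study Procedures:** after training, "the post-test session will repeat the motor and neural measures performed during baseline". The documents therefore establish two motor measurements per participant. Whether motor tests are also done at the training sessions is not stated.
- **Number of Participants:** "The sample size (n=30) was selected to ensure there was sufficient data given issues in data quality or participant retention". The only benchmark is an fMRI one: "it is recommended that there be at minimum 12 participants in each group".

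No section names a baseline covariate, a constraint on the baseline means, or the model term that carries the treatment effect. None gives an SD, a baseline-post correlation or a motor effect size.

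**The concern.** When a randomised trial measures an outcome once before and once after treatment, the baseline can be used in two common ways. It can be subtracted, which fixes its slope at 1, or its slope can be estimated, as in ANCOVA. A group-by-session model with baseline as one level of the outcome does the first. Unless baseline and post-test values are very highly correlated, subtraction removes more of the baseline than it should and adds noise.

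With 30 participants or fewer, and a sample size not built on a motor effect, precision on the primary motor outcome is scarce. The baseline is collected anyway. At stake is the width of the interval around the real-minus-sham difference, and how far a chance baseline difference between small arms moves the estimate.

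**Working it through.** **The plan's own figure.** The only figure is n=30, and no power calculation accompanies it. As arithmetic, 2 × 12 = 24 and 24/0.8 = 30, so 30 is consistent with the benchmark plus 20% loss; the 20% is inferred. I use N=30 and N=24 as the range of evaluable participants.

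**Assumptions (none stated in the documents).** 1:1 allocation, normal data, two-sided 5%. ρ is the baseline-post correlation and k is post SD divided by baseline SD.

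**Step 1: what the interaction tests.** With two sessions and complete data, the group-by-session interaction is the two-sample test on change scores. In one simulated dataset the mixed model and the change-score test both gave a statistic of −1.326. If post-tests are missing, a mixed model with free baseline means departs slightly from the change-score contrast: with 6 of 30 post-tests missing, one simulated trial gave 0.381 against 0.427. It still does not use the fact that randomisation makes the arms' baseline means equal in expectation.

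**Step 2: variances.** In units of baseline variance × 2/(number per arm):

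- change score: 1 + k² − 2ρk
- ANCOVA: k²(1 − ρ²) × (N − 3)/(N − 4), where the last factor is the cost of estimating one slope

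Since 1 + k² − 2ρk = k²(1 − ρ²) + (1 − ρk)², the change score carries an excess of (1 − ρk)², which ANCOVA replaces with a small estimation cost.

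**Step 3: equal SDs (k = 1), N=30.** The factor is 27/26 = 1.0385. At ρ = 0.5 the change score gives 2 × 0.5 = 1.0 and ANCOVA gives 0.75 × 1.0385 = 0.779, a ratio of 1.28. The CI column also counts the lost degree of freedom. The power column is ANCOVA's power where change scores have 80%.

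| ρ | Variance ratio, change/ANCOVA, N=30 | Same, N=24 | ANCOVA 95% CI, N=30 | ANCOVA power, N=30 |
|---|---|---|---|---|
| 0.5 | 1.28 | 1.27 | 12% narrower | 88.7% |
| 0.6 | 1.20 | 1.19 | 9% narrower | 86.6% |
| 0.7 | 1.13 | 1.12 | 6% narrower | 84.6% |
| 0.8 | 1.07 | 1.06 | 3% narrower | 82.5% |
| 0.9 | 1.01 | 1.00 | 1% narrower | 80.4% |
| 0.95 | 0.99 | 0.98 | 1% wider | 79.4% |

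Simulation reproduces the N=30 ratios to within 0.002.

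**Step 4: break-even with equal SDs.** Setting 2(1 − ρ) = (1 − ρ²)(N − 3)/(N − 4) gives ρ = 2(N − 4)/(N − 3) − 1. That is 52/27 − 1 = 0.926 at N=30 and 40/21 − 1 = 0.905 at N=24.

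**Step 5: unequal SDs, N=30.**

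- k = 0.9: variance ratios 1.44, 1.28 and 1.19 at ρ = 0.5, 0.7 and 0.9. ANCOVA is better at every ρ, because the unadjusted ratio is smallest at ρ = k, where it is 1/k² = 1.235, and 1.235/1.0385 = 1.19.
- k = 1.1: 1.18, 1.05 and 0.96. Change scores are slightly more precise for ρ between about 0.79 and 0.96.

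**Step 6: ANCOVA's worst case.** The excess vanishes at ρk = 1, leaving ANCOVA only its cost. The CI factor is √(27/26) × 2.052/2.048 = 1.021 at N=30 and √(21/20) × 2.080/2.074 = 1.028 at N=24.

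**Step 7: chance imbalance.** At 15 per arm the baseline difference has SD √(2/15) = 0.365 baseline SDs and exceeds 0.5 SD in about 17% of randomisations. The change score over-corrects it by (1 − ρk) times its size. With k = 1, a 0.5 SD imbalance shifts the estimate by 0.25, 0.15 or 0.05 SD at ρ = 0.5, 0.7 or 0.9. The shift favours the arm that starts worse only when ρk is below 1; above 1 it reverses.

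**Step 8: validity.** Simulated type I error was 4.9% to 5.1% for change scores and 4.8% to 5.1% for ANCOVA. Both estimates are unbiased under randomisation.

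**The case against.** The strongest reply is that nothing here is an error. Mixed ANOVA on group and session is a standard analysis that answers the stated question about change. This stands.

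Next, the gain depends on a correlation that the documents do not give. "Patients who have had a stroke more than 6 months previously", no severity limits beyond some remaining movement in the limb, and only three training sessions all make a high correlation plausible. At 0.8 the interval narrows by 3%, and at 0.9 by about 1%. This also stands, and it limits how hard the point can be pressed. It does not remove the point, because the possible loss is capped at 2% to 3% while the possible gain is several times that.

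The plan also allows a linear mixed model. Fitted with equal baseline means, it would recover about the ANCOVA precision. The plan neither states nor excludes that constraint, and a protocol summary that is brief about model terms is weak evidence of a deliberate change-score analysis.

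Four stronger readings are tempting, and the documents do not support them:

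- *Baseline is ignored.* It is not; the interaction adjusts for it with a slope of 1.
- *The test is biased or its error rate inflated.* Conditional on a large chance imbalance the false-positive rate does exceed 5%, but it falls below 5% when imbalance is small, and it averages 5.0%.
- *ANCOVA always wins.* It does not above the break-even correlation, or over part of the range when the post-test SD is the larger.
- *The plan would test the group main effect.* No contrast is named, so this cannot be said either.

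**Conclusion.** The point holds as a cheap efficiency improvement, not as the correction of an invalid test. The criticised contrast is inferred from the definition of the primary motor outcome, and its identity with the change-score test needs complete data. The break-even correlations of about 0.93 and 0.90 rest on equal SDs, normality and 1:1 allocation. Within those assumptions the benefit at N=30 runs from a worthwhile 12% reduction in interval width at a correlation of 0.5 to nothing useful at 0.9 or above. Where this trial falls in that range cannot be determined from the documents, so confidence that the change would make a material difference is moderate. The case for making it rests on the asymmetry: the loss is bounded and small whatever the correlation and SDs turn out to be.

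**What to change.** For each motor outcome measured at baseline and post-test, pre-specify one of two analyses:

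1. ANCOVA of the post-test value on group, adjusting for that measure's own baseline.
2. A linear mixed model with baseline means constrained equal across arms and an unstructured covariance. This also keeps participants whose post-test is missing.

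State that the treatment effect is the adjusted real-minus-sham difference at post-test, reported with its 95% CI. Apply this to whichever motor measure is named primary. It also settles which model term is the test.

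The cost is one sentence of analysis wording and one error degree of freedom (27 instead of 28 at N=30; 21 instead of 22 at N=24). No new data are needed. The worst-case interval is about 2% wider at N=30 and 3% wider at N=24.
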